3.4 Endline

Endline data collection will happen approximately six months after the JIC implementation and will administer the same questions to the same grades identified at baseline. At this point, the endline is scheduled to take place in October 2017.

14 Empirical Analysis

Our primary outcomes of interest are knowledge and self-reported behavior. To assess the degree to which the JIC improved both outcomes, we will create an overall index that standardizes all our outcome variables. This includes all questions in sections B1, B2, B3, and B4. In section C, this includes all questions, but question C1-8. In a second step, we will split the overall index into a self-reported behavior (section A and B), and a knowledge index (section C). In a third step, we will split the index further into the following topics: family planning knowledge (B1), condom knowledge (B2), HIV/Aids knowledge (B3), STIs knowledge (B4), sex behavior (C1), self-reported testing behavior (C2), and self-reported health access behavior (C3). To account for the networked nature

of the trial, we estimate the overall effects, total effects, spillover effects, and direct effects of the JIC on our main index and on our sub-indexes, separately for the three targeting strategies and across targeting strategies.

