C1-2	When was that?	1 month ago 2 or 3 months ago 3-6 months ago 6-12 months ago More than 12 months ago
C1-3	In the past 6 months, have you been to the health facility as a patient?	Yes No
C1-4	(Only males) Are you circumcised?	Yes → C1-6 No
C1-5	When were you circumcised?	1 month ago 2 or 3 months ago 3-6 months ago 6-12 months ago More than 12 months ago
C1-6	Have you ever had sexual intercourse?	Yes → C1-8 No → C1-7

C1-7	What is the main reason that you have not had sex? → After, move to section C2.	No opportunity yet No sex before marriage Afraid of getting pregnant Afraid of getting diseases I want to be abstinent Don't know
C1-8	What was the main reason you have had sex?	Married Love Fun/curiosity Friend influenced me I received money in return I wanted to get pregnant I was forced Don't know
C1-9	How many sexual partners have you had in the last 12 months?	0 1 3-5 More than 5
C1-10	Do you have a steady sexual partner?	Yes No
C1-11	The last time you had sex, did you or your partner use a condom?	Yes No → C1-13.
C1-12	Do you use condoms every time you have sex?	Yes No
C1-13	Are you currently using any family planning method or contraception?	Yes No

Section C2: HIV testing Now, we are going to ask you questions about HIV testing.		
C2-1	Have you ever been tested for HIV?	Yes No → C3
C2-2	In the last six months, have you been tested for HIV?	Yes No → C3

C2-3	How many months ago was that?	1 month ago 2 or 3 months ago 3-6 months ago 6-12 months ago
C2-4	Do you know your test result?	Yes No

Section C3: Youth-friendly corners

Now, we have two questions about youth-friendly corners.

C3-1	Have you ever heard of a youth friendly corner at the health facility?	Yes → No D
C3-2	In the past 12 months, have you visited a youth friendly corner at the health facility?	Yes No

Section D: JIC (endline only)

Now, we have a few questions about the Join in Circuit (JIC).

D1	Are you currently wearing a wristband from the JIC?	Yes No
D2	Have you participated in a Join-In Circuit run in the last six months?	Yes → D5 No
D3	Have you heard about the Join-In-Circuit?	Yes No
D4	Did any of your friends talk to you about the JIC or things they learned at the JIC? → After question, skip to D12	Yes No
D5	On a scale from 1 to 5, how interesting did you find the JIC? 1 means you didn't find it interesting at all and 5 means you found it very interesting.	Number _____

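### The behaviour items in the indices are mostly asked of only some students, no student can have a complete index, and the plan gives no scoring for items not asked

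*SAP*

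**What the plan says.** Section 4 (Empirical Analysis) names knowledge and self-reported behaviour as the primary outcomes and states that "we will create an overall index that standardizes all our outcome variables". On the knowledge side, "This includes all questions in sections B1, B2, B3, and B4". On the behaviour side, "In section C, this includes all questions, but question C1-8". The index is then split in two, and split again by topic, with C1, C2 and C3 each an index of its own. Section 4.1 compares these scores between all students in treated schools and all students in control schools.

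The questionnaire in Section 6.2 is routed. C1-6 asks "Have you ever had sexual intercourse". A student who answers no goes to C1-7, which carries the instruction "After, move to section C2". A student who answers yes goes to C1-8 and on to C1-9 to C1-13. Section C2 and section C3 have gates of the same kind.

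Neither Section 4 nor the robustness checks in Section 4.4 say how an item that was not put to a student enters the score. (Section 4 labels section C as knowledge and sections A and B as behaviour, the reverse of Section 3.3. The main, C1, C2 and C3 indices are affected whichever label is meant.)

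**The concern.** An inclusion rule that lists items is enough only if every student is asked every item. Here most behaviour items do not exist for many students, so the analyst has to choose a scoring rule that the plan does not give, and the choice changes what is estimated.

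The natural default is to average whatever was answered. Then "The last time you had sex, did you or your partner use a condom" counts only among students who have had sex by endline, and "Do you know your test result" counts only among those tested in the last six months. Endline is planned about six months after the JIC, so these statuses can change after the intervention. Section 1 gives HIV testing uptake and demand for health services as aims of the JIC. The students who answer such an item in treated and control schools need not be comparable, although the schools were randomised.

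**Working it through.** The plan gives no figure to reproduce here. The check is a count of items and routes, followed by arithmetic with assumed inputs.

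**Items and routing (Sections 4 and 6.2)**

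| Index | Items | Routed items | Share |
|---|---|---|---|
| C1 | 13 − 1 (C1-8) = 12 | C1-2, C1-4, C1-5, C1-7, C1-9 to C1-13 = 9 | 75% |
| C2 | 4 | C2-2, C2-3, C2-4 = 3 | 75% |
| C3 | 2 | C3-2 = 1 | 50% |
| Section C | 18 | 13 | 72% |

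C1-4 is put to males only. It is missing by design but is not a status that the JIC could change.

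Section B adds 17 + 7 + 12 + 13 = 49 items, so the main index has 49 + 18 = 67. The 13 routed behaviour items are 13/67 = 19% of it, and C1-9 to C1-13 are 5/67 = 7%. Section B has awareness gates too: B1-9, B1-12 and B1-15 (two items each), B3-1 (11 items) and B4-1 (12 items), together 6 + 11 + 12 = 29 items.

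**Most items a student can answer**

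- Male, has had sex: 18 − 1 (C1-7) = 17 of 18, and 11 of 12 in C1.
- Female, has had sex: 17 − 2 (C1-4, C1-5) = 15 of 18, and 9 of 12 in C1.
- Male, never had sex: 18 − 5 (C1-9 to C1-13) = 13 of 18, and 7 of 12 in C1.
- Female, never had sex: 13 − 2 = 11 of 18, and 5 of 12 in C1.

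Every route through section C was enumerated, with the skips at C1-1 and C1-4 read both ways (arrow on yes, arrow on no). None gives all 12 C1 items or all 18 section C items.

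**Direction of bias in a routed item (all inputs assumed)**

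1. The JIC leaves condom use unchanged but prevents debut in a share *d* of students. A share *p* of control students has had sex. Condom use is *k* among those who have sex anyway and *m* among those whose debut is prevented. The item, among those asked, then differs by *k* − [(*p* − *d*)*k* + *dm*]/*p* = *d*(*k* − *m*)/*p*. With *k* = 50%, *m* = 20–30%, *p* = 10–40% and *d* = 1–5 points, the smallest value is 0.01 × 0.20/0.40 = 0.5 points and the largest 0.05 × 0.30/0.10 = 15 points, in favour of the JIC.
2. In control, 30 of 100 have had sex and 12 used a condom: 12/30 = 40%. The JIC delays debut in 6. If 4 of the 6 would have used a condom, the item is 8/24 = 33%. If 40% of them would have, it is 9.6/24 = 40%. If 1 would have, it is 11/24 = 46%.
3. For C3-2: in control, 20 of 100 have heard of youth-friendly corners and 10 visited one, 10/20 = 50% of those asked. In treated schools 40 have heard and 14 visited, 14/40 = 35%. Visits rise by 4 per 100 while the item falls by 15 points.

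The sign depends on who crosses the gate, and the documents give no rates for debut, testing or awareness.

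**The case against.** The strongest reply is that the plan lists which items belong to the index and does not commit to averaging, dropping or filling. Bias arises only under some scoring rules, and one fixed value for students not asked would avoid it. That is right, and it is why the defect is stated as an unscored, incomplete index rather than as a bias already built in. But the rule as written cannot be computed for any student without a further choice.

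The size may also be modest. For students who had sex, were tested or had heard of the service before the JIC, the status is pre-treatment. Delayed debut is not among the aims in Section 1. And 114 of the 133 baseline schools are primary (grade 6), where the sex items probably apply to few students. This limits the effect through C1-6 on the main index. It does not help the C2 and C3 indices, whose gates are testing and service awareness.

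Three stronger readings are tempting and should not be drawn:

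- **That an index is shown to move the wrong way.** The illustrations concern single items, and the gate item is in the index too. Take example 2 with 4 of 6 (never had sex / condom / no condom: 70/12/18 in control, 76/8/16 treated), standardise C1-6 and C1-11 to control, and code never had sex as favourable. Averaging available items gives 0.70 × 0.655 − 0.12 × 0.151 − 0.18 × 1.172 = 0.229 in control and 0.76 × 0.655 − 0.08 × 0.151 − 0.16 × 1.172 = 0.298 treated. The two-item index improves.
- **That filling blanks with zero scores abstinent students as condom non-users.** The items are standardised, so a zero entered afterwards is the mean. The statement would hold only for raw zeros entered beforehand.
- **That, without C1-7, only circumcised boys could have a complete score.** This depends on which answer the C1-4 skip belongs to, which the extracted text does not settle.

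**Conclusion.** The point holds as a defect in how the outcome is defined. Thirteen of the 18 behaviour items are routed, C1-7 and C1-9 to C1-13 exclude each other, and no student can have a complete C1, section C or main index. This rests only on Section 4 and the questionnaire, with no assumed figure.

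That averaging the answered items would bias the comparison is conditional. It requires that rule to be chosen and the JIC to change debut, testing or awareness by endline. Direction and size are then unknown: under the assumed inputs a single item can shift by 0.5 to 15 points in favour of the JIC, or fall by 7 or 15 points. The effect is diluted in the main index if items are weighted equally (an assumption, as no weights are stated). It is of most concern for the C1, C2 and C3 indices.

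**What to change.** In Section 4, replace the rule that takes all section C questions except C1-8 with behaviour items defined for every student.

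- **Keep** the items asked of everyone: C1-1, C1-3, C2-1, C3-1, and C1-6 with its favourable direction stated.
- **Recode** the routed items: unprotected last sex (C1-6 yes and C1-11 no; never had sex counts as no); multiple partners in the last 12 months (never had sex counts as no; cut-off checked against the C1-9 answer options in the fielded instrument, since the extracted list goes from 1 to 3-5); tested in the last six months (never tested counts as no); tested in the last six months and knows the result (otherwise no); visited a youth-friendly corner (never heard counts as no).
- **Keep as missing**, not as no, any refusal or skipped answer at a gate. The introduction to C1 lets students skip questions.
- **Leave out as scored items** the reason item C1-7, as C1-8 already is, and the date items C1-2, C1-5 and C2-3. Report circumcision among boys separately, and C1-10, C1-12 and C1-13 descriptively.
- **Section B:** score the items behind B1-9, B1-12, B1-15, B3-1 and B4-1 as not known when the gate answer is no. Otherwise the main index stays incomplete.

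This gives 5 kept and 5 recoded items, 10 in all. The cost is SAP wording and recoding. No new question is needed, and in the plan the endline is still to come. The downside is that some detail among sexually active students moves to secondary description.

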3.3 Outcome measurement

The questionnaire, administered during the base- and endline of the project, includes four substantive sections. The first section (A) administers demographic questions (e.g., gender, religion, etc.). The second section (B) administers questions pertaining to knowledge about sexual and reproductive health. This includes family planning (B1), condoms (B2), HIV/Aids (B3), other STIs (B4). The third section (C) administers questions about self-reported behavior. This includes sex (C1), HIV testing (C2), and access of youth-friendly corners (C3). The final section, only asked during the endline, includes questions about the JIC.

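### The second-step rule swaps the labels of the knowledge and behaviour indices, and the unordered item C1-7 stays in three indices without a recode

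*SAP*

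**What the plan says.** Section 4 (Empirical Analysis, opening paragraph) names knowledge and self-reported behaviour as the primary outcomes and builds indices in three steps.

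- **Step 1, overall index.** For section B: "This includes all questions in sections B1, B2, B3, and B4". For section C: "In section C, this includes all questions, but question C1-8". Section A is not included.
- **Step 2, two summaries.** The plan states that "we will split the overall index into a self-reported behavior (section A and B), and a knowledge index (section C").
- **Step 3, seven topics.** B1 to B4 are each called knowledge, and the rest are "sex behavior (C1), self-reported testing behavior (C2), and self-reported health access behavior (C3").

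Section 3.3 describes the questionnaire: "The first section (A) administers demographic questions"; "The second section (B) administers questions pertaining to knowledge about sexual and reproductive health"; "The third section (C) administers questions about self-reported behavior".

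All these indices are used, since "we estimate the overall effects, total effects, spillover effects, and direct effects of the JIC on our main index and on our sub-indexes". Section 4.1 adds an exploratory hypothesis that the knowledge index improves more than the behaviour index. Footnote 3 in that section lists A1 to A9 as individual-level covariates.

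**The concern.** The step 2 sentence is the only definition of the two indices that summarise the stated primary outcomes, and it assigns the sections the wrong way round. An analyst who followed it literally would report the effect on the section B items as a behaviour effect and the effect on the section C items as a knowledge effect. The exploratory comparison of the two would change direction. An analyst who did the sensible thing would formally depart from the plan, and section 5 promises that every deviation will be made explicit.

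The second matter is an item-list choice. C1-8 asks the main reason for having had sex and is excluded. C1-7 asks the main reason for not having had sex, has the same form, and is kept. The only scoring instruction is that outcome variables are standardised. C1-7 has no order, no correct answer and no stated desirable direction, so standardising its category codes has no meaning.

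**Working it through.** **Labels, side by side**

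| Section | Section 3.3 | Instrument heading (6.2) | Section 4, step 3 | Section 4, step 2 |
|---|---|---|---|---|
| A | demographics | demographics | not used | behaviour |
| B | knowledge | knowledge | knowledge | behaviour |
| C | behaviour | behaviour | behaviour | knowledge |

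Step 2 stands alone against three other places.

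**Item counts (from the instrument, section 6.2)**

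- B1 17, B2 7, B3 12, B4 13: 17 + 7 + 12 + 13 = 49.
- C1 13, C2 4, C3 2, less C1-8: 13 + 4 + 2 - 1 = 18.
- Overall index: 49 + 18 = 67.
- Step 2 with section A (9 items) taken at its word: (9 + 49) + 18 = 76, which is 9 more than the 67 items being split. Splitting an index cannot add items, so the reference to section A cannot be carried out.
- Step 2 without section A: the index labelled behaviour holds the 49 B items and no C item; the index labelled knowledge holds the 18 C items and no B item. If the true difference (knowledge effect minus behaviour effect) is d, the difference computed under these labels is -d.

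**Where C1-7 enters**

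With equal item weights (an assumption; the plan gives none), its share is 1/67 = 1.5% of the overall index, 1/18 = 5.6% of the section C index and 1/12 = 8.3% of the C1 index. The 12 are the 13 C1 items less C1-8. C1-7 is asked only of students who answer no to C1-6.

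**Illustration of the numbering problem (response shares assumed, not from the plan)**

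Suppose the six reasons are equally common in control schools, and treatment moves 10 percentage points from the option of no opportunity to that of fear of disease.

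- Codes 1 to 6 with equal shares: SD = sqrt(35/12) = 1.708.
- Listed order (option 1 to option 4): 0.1 × (4 - 1)/1.708 = +0.18 SD.
- Over all 720 numberings, the extremes are ±0.1 × 5/1.708 = ±0.29 SD. Half are negative, because reversing any numbering reverses the sign.

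The same response shift can therefore count as an improvement or as harm. The extreme numbering carries through to the indices as follows, if every student took this branch and items are averaged:

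- Skipped items scored, so that the full item count is the divisor: 0.293/12 = 0.024 in the C1 index, 0.293/18 = 0.016 in the section C index, 0.293/67 = 0.004 in the overall index.
- Skipped items left missing: a student who has not had sex is put only 4 to 7 C1 items. Girls get C1-1, C1-3, C1-6 and C1-7, with or without C1-2 (4 to 5); boys also get C1-4, with or without C1-5 (5 to 7). The C1 index then moves by 0.293/7 = 0.042 to 0.293/4 = 0.073.

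The plan does not say which treatment of skipped items applies.

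**The case against.** The strongest reply on the labels is that this is an obvious slip. The correct mapping stands in section 3.3, in the instrument and in the very next sentence, so no careful analyst would be misled. No estimate changes in value; two names are exchanged, and the hypothesis affected is one that the plan itself calls exploratory. This largely stands and sets the severity. It does not remove the point, because the sentence is an operative definition in a pre-analysis plan and is wrong on any reading.

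On C1-7, the reply is that the plan never says raw codes will be standardised. The knowledge items are printed as 1, 2, 3 for true, false and don't know, so some recoding must be presupposed throughout. This also stands: missing item coding is general. C1-7 remains the clearest case because, unlike a true/false knowledge item, it offers nothing from which a recode could be inferred, while its twin was removed by name.

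Two stronger readings are tempting. A reader might infer that the primary results are compromised. The documents do not support that: the overall index and the seven topic indices are not touched by the label swap, and C1-7 is 1 of 67 items in the overall index. A reader might also infer that, because many items follow a filter question, the sign of the knowledge effect is undetermined. That would need response shares that the plan does not give, and some skip arrows in the available text are garbled, so no such conclusion can be drawn.

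**Conclusion.** Both parts hold, at low severity. The step 2 rule in section 4 is wrong as written: it exchanges the labels of the two primary-outcome summaries, names a section that is not in the index, and reverses one exploratory comparison. The intended meaning is recoverable from the rest of the plan.

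C1-7 is an unordered item kept in three indices with no recode. Its influence on the overall index is negligible. In the C1 index it is small if skipped items are scored and larger if they are left missing (about 0.02 against 0.04 to 0.07 in the illustration). Those figures rest on assumed response shares, the most extreme numbering, equal item weights and all students being on the branch that has not had sex. They show the mechanism and are neither forecasts nor general limits. That the sign is arbitrary needs none of these figures, only that the options have no order.

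**What to change.** Rewrite the second step in section 4: knowledge index = B1-B4; self-reported behaviour index = C1-C3 without C1-7 and C1-8; section A as covariates only. Drop C1-7 from the overall index and the C1 index as well, or state a binary or ordered recode for it before the endline data are seen. If it is simply dropped, the counts become 18 - 1 = 17 (behaviour), 67 - 1 = 66 (overall) and 12 - 1 = 11 (C1).

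The cost is one rewritten sentence and one change to the item list, with no effect on design or data collection. The downside is that the reasons for not having had sex leave the index; they can be tabulated separately by arm.

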4.1 Overall effect

H1: We hypothesize that the JIC improves the main and sub-index scores for students in treated schools.

Separately for each targeting strategy, we estimate the overall effect of the JIC by comparing all students in treated schools to all students in control schools,

$$Y_{ij} = \beta_0 + \beta_1 T_j + \beta_2' X_{ij} + \epsilon_{ij}$$

where Y_{ij} represents the respective index for individual i in school j ; X_{ij} marks a vector of salient predictive school- and individual-level pre-treatment covariates³.

T_j is a dummy variable denoting whether a given school was treated or not. To ease interpretation and in line with [Freedman \(2008\)](#), we will use ordinary least squares. For selected robustness tests, we will also include school-random effects. Given that randomization is at the level of the school, we will cluster standard errors at the school level. Moreover, given that we pre-specify one main hypothesis, we will not adjust uncertainty levels for multiple comparisons.

In addition, we pre-register the following additional exploratory hypotheses:

- The JIC improves the knowledge index more strongly than the self-reported behavior index.

³Specifically, at the school-level we include: Students, Choma, Primary, Rural, JIC before, GRZ, Private, Nearest DEBS, Nearest YFC, Nearest HF. At the individual-level, we include age (A1), gender (A2), grade (A3), religion (A4), father's primary job (A5), father's literacy (A6 and A7), parents' marital status (A8) and mother tongue (A9).

- 1• The JIC improves the main index more strongly in urban areas as compared to rural areas.

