4.2 Targeting effect

H2: We hypothesize that the overall effect of the JIC is strongest under edge-central targeting, intermediate under indegree targeting, and weakest under random targeting.

We estimate the contribution of targeting to the overall effect with the following equation:

$$Y_{ij} = \beta_0 + \beta_1' S_j + \beta_2 X_{ij} + \epsilon_{ij}$$

where S_j is a vector of indicator variables for random, indegree, and edge central targeted schools, and differences between the elements of β_1 evaluate the differences between targeting strategies.

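### Multiplicity adjustment is waived because there is one main hypothesis, but H1 maps to three tests on the main index alone, with no pooled model and no rule for what counts as support

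*SAP*

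**What the plan says.** Section 4.1 gives a single reason for not correcting: "given that we pre-specify one main hypothesis, we will not adjust uncertainty levels for multiple comparisons". The hypothesis in question, in the same section, reads "H1: We hypothesize that the JIC improves the main and sub-index scores for students in treated schools". It names no targeting strategy and includes the sub-indexes.

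The test is equation (1), with a treated-or-not indicator for the school. It is introduced with "Separately for each targeting strategy, we estimate the overall effect of the JIC", the comparison being with control schools.

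The outcomes are defined in Section 4 (Empirical Analysis). First comes a single index: "To assess the degree to which the JIC improved both outcomes, we will create an overall index that standardizes all our outcome variables". Then "In a second step, we will split the overall index" introduces two domain indexes (knowledge and behaviour), and a third step produces seven topic indexes (B1 to B4 and C1 to C3). That makes one main index and nine sub-indexes. The same section says effects will be estimated "on our main index and on our sub-indexes, separately for the three targeting strategies and across targeting strategies".

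The SAP states no significance level, no sidedness, and no rule for when H1 is supported.

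**The concern.** A waiver on the ground of one hypothesis is sound when that hypothesis is settled by one test, or by a rule requiring every test to succeed. Here one sentence is answered by three estimates on the main index and by thirty if all ten indexes are counted. The plan does not say how those estimates combine into a verdict.

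At stake is the false-positive risk of the headline claim that the JIC works. H1 is worded for the JIC in general, while the estimates are specific to a strategy. If one of three strategies reaches significance, an author could report either that this strategy works or that the JIC works. The strategy-specific statement has its nominal error rate and the general one does not. As written, the choice can be made after the endline data are seen, which a pre-analysis plan is meant to prevent.

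**Working it through.** The SAP states no alpha, power or familywise error rate, so there is no figure to reproduce. Assumed throughout: two-sided 5% per test, no true effect (for error rates), and normal tests on school-level means. Covariates, unequal school sizes and small-sample corrections are ignored.

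**Inputs**
- As randomised (Section 2.2): 34 schools per treatment arm; 34 + 34 = 68 control schools.
- Reached at baseline (Section 3.1): 98 treated schools, or 98/3 = 32.7 per arm; 28 + 7 = 35 control schools.
- Control 1 only, since the Section 2.2 footnote foresees excluding schools in robustness tests: 28 control schools.
- Indexes (Section 4): 1 + 2 + 7 = 10. Strategies: 3. H1 tests: 10 × 3 = 30.

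**Main index, any one of three strategies counts**

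With independent tests the risk would be 1 − 0.95³ = 14.3%. The three tests share a control group, so they are correlated with ρ = n_t/(n_t + n_c), and

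risk = 1 − ∫ [Φ((c − √ρ·x)/√(1−ρ)) − Φ((−c − √ρ·x)/√(1−ρ))]³ φ(x) dx, with c = 1.96.

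| Schools per arm vs control | ρ | Any of three, two-sided 5% | Favourable direction only (2.5% per test) |
|---|---|---|---|
| 34 vs 68 (randomised) | 0.333 | 13.5% | 6.8% |
| 32.7 vs 35 (baseline) | 0.483 | 12.7% | 6.3% |
| 32.7 vs 28 (Control 1 only) | 0.538 | 12.3% | 6.1% |

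The inflation does not hinge on 5%. At two-sided 1% the risk is 2.7 to 2.9%, and at 10% it is 23 to 26%.

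**Main index, each strategy its own claim**

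5% for each claim; no inflation.

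**One strategy, any of ten indexes counts**

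This was simulated with seven equally correlated topic indexes, the domain and overall indexes being their averages. The topic correlation is assumed, as the SAP gives none. The risk is 34% at correlation 0, 21% at 0.6 and 9% at 0.95. As a check on the first figure, seven independent tests alone give 1 − 0.95⁷ = 30.2%, and the three averages add a little more.

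**One pooled test on the main index (98 vs 35 schools)**

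Type I error is 5%, so the waiver would then be true.
- Standard errors in units of the between-school SD: pooled √(1/98 + 1/35) = 0.197; single strategy √(1/32.7 + 1/35) = 0.243. The ratio is 0.81, so the detectable average effect is 19% smaller.
- Take an effect giving 80% power for one unadjusted strategy test: (1.960 + 0.842) × 0.243 = 0.682.
- If all three strategies have it: 0.682/0.197 = 3.46, and Φ(3.46 − 1.96) = 93%.
- If only one has it: the average effect is 0.682/3 = 0.227; 0.227/0.197 = 1.15, and Φ(1.15 − 1.96) = about 21%.

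**Dunnett on the three main-index tests (baseline schools)**

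The critical value is 2.352, or p < 0.0187 per test. The detectable single-strategy effect rises by (2.352 + 0.842)/(1.960 + 0.842) = 1.14, or 14%. At the effect above, power for that strategy falls from 80% to Φ(2.802 − 2.352) = 67%.

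**The case against.** The strongest reply is that the plan already leans towards one claim per strategy. The first research question in Section 1 is asked for each strategy, Section 4.1 fits the model strategy by strategy, and the strategies are treated as distinct interventions to be ranked. On that reading, judged on the main index, no adjustment is needed. This stands, and it makes the 12 to 13.5% conditional. It does not rescue the stated reason: three separate claims are not one main hypothesis, and H1 still speaks of the JIC without naming a strategy.

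Second, the outcomes are ranked. Building one overall index first and splitting it afterwards is itself a guard against multiplicity. This also stands in part, but H1 puts the main and sub-indexes on the same footing, and no testing order is attached to the splits.

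Third, Section 4 may hint at a pooled analysis when it speaks of estimating effects across strategies. The phrase is ambiguous. No pooled sample or equation follows, and Section 4.3 uses the same wording for comparing strategies. Equation (2) holds all three arms, but with separate coefficients that the plan uses only for differences between strategies.

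Two stronger inferences are not supported. A reader might count all thirty H1 tests and conclude that a false positive is likely; nothing in the SAP says that any one of thirty suffices, and the result would depend heavily on assumed correlations. A reader might also take H2 as proof that there is more than one main hypothesis. H2 answers a different question, can be read as subsidiary, and does not change the error rate for H1.

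**Conclusion.** The concern holds in a limited form. The reason given for the waiver is contradicted by the plan's own wording of H1 and by its strategy-by-strategy estimation, and no decision rule fills the gap. The separate estimates remain valid; what is undefined is the error rate of the general claim.

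The size depends on the rule adopted: no inflation if each strategy is a separate main-index claim; about 12 to 13.5% against 5% (6.1 to 6.8% against 2.5% in the favourable direction) if any strategy may support the general claim; and, within one strategy, about 9 to 34% if any of its ten indexes may count. These figures rest on an assumed two-sided 5% level and the simplified school-level model, and the last also on assumed correlations. It would be wrong to report 12.7% as the trial's error rate, because the SAP neither adopts nor excludes the rule behind it. The point should be settled before the endline data are analysed.

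**What to change.** 1. In Sections 4 and 4.1, name the main index as the confirmatory outcome for H1 and label the nine sub-indexes secondary.
2. Write one pooled model as the single test of H1: equation (1) with all three treated arms against control, main index, school-clustered standard errors, and stated alpha and sidedness. The waiver then becomes true for H1.
3. Report the three strategy-specific main-index tests after it, as separate claims about each strategy, and do not draw a general conclusion about the JIC from one of them.
4. If a single strategy's result is instead meant to support the general claim, apply Holm or Dunnett to the three main-index tests and delete the one-hypothesis justification.

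Cost: one extra model and a few sentences; no new data. The pooled test is the stronger one if the strategies work about equally (93% power where a single-strategy test has 80%) but weak if only one works (about 21%). The authors expect unequal effects, so they should weigh this. Under step 4, Dunnett raises the detectable single-strategy effect by about 14%.
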